### Statistical Methods

*Design:* Caregivers will be randomized into two groups: Active In-Home Technology System and Limited In-Home Technology System. Subjects will be randomized 1:1. Randomization of participants in each group will be determined by People Power employees. Analyses of caregiver health and well-being will use 2 X 3 (Condition [active treatment vs control] X Time [time 1 vs time 2 vs time 3]) mixed model analysis of variance. In all analyses, significant main effects and interactions will be decomposed using a priori or post hoc comparisons depending on whether they are hypothesized or not. Bonferroni corrections will be used to control for Type I error resulting from multiple comparisons. Statistical Power. Tests of hypothesized Group differences (active treatment vs control condition) for caregiver health and well-being will have .80 power to detect a medium effect size (one-tailed, alpha = .05). Using repeated measures analysis of variance, tests of the interaction of Condition (2 groups) X Time (3 assessments) will have power of .99 to detect a medium effect size (correlation between repeated measures  $r = .5$ , alpha = .05).

*Analysis:* Descriptive statistics will be used to summarize all the clinical characteristics and demographic outcomes. These will be summarized overall, by treatment group, by assessment time, and by treatment group and time. Continuous variables will be summarized using means, standard deviations, and ranges. Categorical data will be summarized by number and percent. To evaluate the treatment effects, we will use repeated measures ANOVAs. The other predictors will be treatment group, and time (baseline, 3-months, and 6-months for caregiver outcomes). To evaluate treatment effects, an interaction term between treatment group and time will be included

to examine treatment group-related differences in the assessments for each outcome. Each significant interaction will be followed up with paired t-tests to examine treatment differences at each set of time points. Although this study involves 4 outcomes, we do not plan formal multiple comparison adjustments if the results fit a coherent pattern that is consistent with the context of similar studies. In this case, each result will reinforce the other, rather than detracting from one another, as required by formal multiple comparisons adjustments such as Bonferroni.

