Conversely, if only one or a very few measures reach statistical significance and their directions and/or magnitudes do not coherently fit with our a prior expectations, then we will note that the result(s) with  $p < 0.05$  lack plausibility and could be due to chance, despite meeting the conventional cutoff for statistical significance.

*Missing Data:* If subjects either cannot or refuse to complete surveys we will use a sensitivity analysis approach in dealing with these missing data by performing analysis with 2 versions of scores: 1) with missing item interpolated using mean replacement by group, and 2) only using responses with 0% missing data. If the results differ for the two approaches, then we will report on the differences.

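### Adjustment across four unranked primary outcomes is waived by an undefined coherence test that can be judged only after the results are seen, so the plan has no defined overall error rate

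*SAP*

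**What the plan says.** The SAP's Primary Outcomes section lists four scales (caregiver burden, depression, anxiety, life satisfaction) and ranks none of them. Under Statistical Methods, the Analysis paragraph evaluates treatment effects by adding a group-by-time interaction "to examine treatment group-related differences in the assessments for each outcome". The alpha given in the power statements is .05.

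Three statements bear on multiplicity:

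- **Design paragraph.** After saying that "significant main effects and interactions will be decomposed using a priori or post hoc comparisons", it adds that "Bonferroni corrections will be used to control for Type I error resulting from multiple comparisons". The family of comparisons is not named.
- **Analysis paragraph, waiver.** "Although this study involves 4 outcomes, we do not plan formal multiple comparison adjustments if the results fit a coherent pattern", the pattern being one "that is consistent with the context of similar studies". The reason given is that "each result will reinforce the other, rather than detracting from one another".
- **Analysis paragraph, converse case.** The trigger is "if only one or a very few measures reach statistical significance and their directions and/or magnitudes do not coherently fit" with prior expectations. Results below 0.05 will then be noted to "lack plausibility and could be due to chance, despite meeting the conventional cutoff for statistical significance". No adjusted threshold is given.

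**The concern.** Whether the four primary tests are adjusted depends on a property of the results. The available text does not say how many scales must be significant, how large the effects must be, which similar studies set the context, or who judges the fit. The SAP's four references are papers on the four scales, not studies of similar interventions. The condition can therefore be assessed only with the results in hand.

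The caveat does not close the gap. As worded it needs two things together: few significant measures and a poor fit. A single significant scale that is judged to fit expectations triggers neither a stated adjustment nor a caveat. Two analysts who both follow the SAP could report that same result differently, one as an unadjusted primary finding and the other as a result needing correction. The error rate attached to the trial's main claim would then depend on a reading chosen after the data are seen.

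**Working it through.** **Inputs.** Four primary outcomes (SAP, Primary Outcomes). One interaction test per outcome with 2 numerator df, from 2 groups and 3 times; alpha .05; repeated-measures correlation .5 (SAP, Statistical Methods). 60 caregivers per arm (Protocol, Randomization). Assumed, because the documents do not give them: the between-outcome correlation r; f = 0.25 and d = 0.5 for a medium effect; the sign of the baseline-to-6-month contrast as the direction of a result.

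**The plan's own figures.** The documents state no overall type I error, so only the power figures can be checked.

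- Interaction: λ = N·f²·m/(1 − ρ) = 120 × 0.0625 × 3/0.5 = 45, with df 2 and 236. Power is above .9999, consistent with the stated .99. If the medium effect is instead entered as λ = N·f² = 7.5, power is .68, which does not match.
- Group difference, one-tailed, d = 0.5, 60 per arm: noncentrality 0.5 × √30 = 2.74, power .86. The stated .80 corresponds to 50 to 51 per arm.

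**Any nominal false positive.**

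- Four independent interaction tests: 1 − 0.95⁴ = 18.5%.
- Any dependence: at most 4 × 0.05 = 20%.
- Interaction plus Condition main effect on each outcome, eight independent tests: 1 − 0.95⁸ = 33.7%, with bound 8 × 0.05 = 40%. By simulation at r = 0.5: 28.9%.

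**Narrower readings at r = 0.** Each test has probability 0.025 of a significant result in the favourable direction.

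- Exactly one significant, and favourable: 4 × 0.025 × 0.95³ = 8.6%.
- At least one significant, every significant result favourable: 0.975⁴ − 0.95⁴ = 8.9%.
- At least two significant, every significant result favourable: 8.92% − 8.57% = 0.3%.
- At least one significant, all four scales pointing favourably: 18.55%/16 = 1.2%.

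**With correlated outcomes.** Simulation under the null, four 2-df tests, equal correlation r; entries in %:

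| Reading | r=0 | 0.3 | 0.5 | 0.7 | 0.9 |
|---|---|---|---|---|---|
| Any significant | 18.5 | 17.5 | 15.8 | 13.3 | 9.6 |
| Any favourable | 9.6 | 9.0 | 8.1 | 6.9 | 4.9 |
| Lone favourable | 8.6 | 7.7 | 6.3 | 4.4 | 2.1 |
| ≥1 significant, all significant ones favourable | 8.9 | 8.5 | 7.7 | 6.5 | 4.6 |
| ≥1 significant, all four scales favourable | 1.2 | 3.5 | 4.8 | 5.3 | 4.4 |
| ≥2 significant, all significant ones favourable | 0.3 | 0.9 | 1.4 | 2.0 | 2.5 |
| Any rejection with Holm | 4.9 | 4.7 | 4.4 | 3.8 | 2.7 |

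Simulating the planned 2 × 3 mixed ANOVA itself, with 60 per arm, gave 18.6% for any significant result at r = 0 and 16.1% at r = 0.5, in line with the first row.

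**Power at the strictest Holm step, 0.05/4 = 0.0125.**

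| Test and assumed effect | α = .05 | α = .0125 |
|---|---|---|
| Interaction, f = 0.25 | >.999 | >.999 |
| Interaction, f = 0.15 (λ = 16.2) | .96 | .88 |
| Interaction, f = 0.10 (λ = 7.2) | .66 | .45 |
| One-tailed group difference, d = 0.5 | .86 | .68 |

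**The case against.** The plan states its approach openly and in advance. Its reasoning, that agreement among related scales strengthens each result, is a recognised argument. Making the waiver conditional implies adjustment otherwise, and the Bonferroni sentence could supply that default. The talk of results reinforcing one another suggests that several agreeing results were meant, so a lone significant scale may never have been intended to qualify. Direction is not wholly open either: the SAP says which end of each scale is worse and powers a one-tailed group difference. Isolated, ill-fitting results will be flagged.

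Much of this stands, and it limits what can be claimed. A reader might infer that 18.5% is the trial's false-positive rate. The documents do not support that, because no rule says one significant scale is enough for success, and some sensible meanings of coherence keep the error below 5%. Nor is 18.5% a ceiling, as the 20% bound and the main-effect calculation show. A reader might also infer that the two multiplicity statements flatly contradict each other. They may, but the Bonferroni sentence follows the one on decomposing effects and may cover only those follow-up contrasts.

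What the objection does not supply is a criterion. Each charitable reading has to be chosen by the analyst, and the text permits the others.

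**Conclusion.** The point holds as an undefined, result-dependent rule for the primary analysis, not as proof of a particular inflated error rate. No overall error rate can be assigned to the plan. How far the candidate meanings of coherence differ depends on the assumed correlation: the requirement of one versus two significant results, all favourable, gives 8.9% against 0.3% at r = 0, 7.7% against 1.4% at r = 0.5, and 4.6% against 2.5% at r = 0.9. A very large ratio between readings therefore needs near-independent outcomes.

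The directional figures apply to the interaction test with the assumed sign convention, not to the one-tailed group-difference test. This should be fixed, and before unblinded results are examined, because a criterion written afterwards cannot restore error control.

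**What to change.** Amend the SAP as follows:

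1. State that the Condition × Time interaction is the sole confirmatory test for each outcome.
2. Apply Holm to the four interaction p-values whatever the pattern of results: compare them, from smallest to largest, with 0.0125, 0.0167, 0.025 and 0.05, stopping at the first failure.
3. Keep coherence with expectations and with similar studies as descriptive discussion that has no bearing on significance.
4. Reconcile the Bonferroni sentence in the Design paragraph by naming its family, for example the within-outcome follow-up contrasts.

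Naming one primary outcome and making the other three secondary is an alternative open to the sponsor, not a required change.

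The change is to wording only, but it has a price in power. The working shows the worst case; Holm loses no more than that. The cost is negligible at f = 0.25 and moderate at f = 0.15. It is larger below that, or if the medium effect was meant in the N·f² sense (.68 falling to .47). If the sponsor also treats the one-tailed group difference as confirmatory and adjusts it, power falls from .86 to .68 and the stated .80 would have to be restated.

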Once consent procedures are complete, caregivers receive a Qualtrics link with their initial questionnaire. Identical Qualtrics questionnaires will be sent via email to caregivers in both research conditions at baseline, 3 months, and 6 months. The three sets of questionnaires will be identical, except the baseline questionnaire will also include a contact information form and "Information about person receiving care."

Randomization:

Sixty caregivers will be randomly assigned to the "active in-home technology" condition of the system and the remaining 60 caregivers will be assigned to the "control" condition. Randomization of participants in each group will be determined by People Power employees after the consent process.

Outcome Measures:

All caregivers—regardless of randomized study condition—complete questionnaires on three separate occasions during this study: baseline, 3-months, 6-months. The four outcome measures are: (a) Zarit Burden Interview-Short Form, a questionnaire measuring caregiver burden (Zarit, Reever, & Bach-Peterson, 1980). 12 items are rated on 0-4 scale. Range: 0-48. No subscales. Higher scores represent worse outcomes; (b) Center for Epidemiological Studies Depression Scale (CES-D), a questionnaire measuring depression (Radloff, 1977). 20 items are rated on a 0-3 scale and summed (range = 0-60). There are no subscales. Higher scores represent worse outcomes. The clinical cut-off is usually set at a score of 16; (c) Beck Anxiety Inventory (BAI), a questionnaire measuring anxiety (Beck, Epstein, Brown, & Steer, 1988). 20 items are rated on a 0-3 scale and summed (range= 0-60). Higher scores indicate worse outcomes. There are no subscales. A score greater than 36 is considered to be clinically significant; and (d) Satisfaction with Life Scale, a questionnaire measuring overall life satisfaction and well-being (Diener, Emmons, Larsen, & Griffin, 1985). 5 items scored on a 1-7 scale and summed (Range = 5-35). Lower scores indicate worse outcomes. A score of 20 is considered neutral with higher scores considered increasingly more satisfied and lower scores considered increasingly more dissatisfied.

Contact initiated by study staff

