## Statistical Analysis Plan

### Primary Outcomes

All caregivers—regardless of randomized study condition—complete questionnaires on three separate occasions during this study: baseline, 3-months, 6-months. The four outcome measures include changes over the 6-month study period for the following scales: Zarit Burden Interview-Short Form, a questionnaire measuring caregiver burden (Zarit, Reever, & Bach-Peterson, 1980). 12 items are rated on 0-4 scale. Range: 0-48. No subscales. Higher scores represent worse outcomes; Center for Epidemiological Studies Depression Scale (CES-D), a questionnaire measuring depression (Radloff, 1977). 20 items are rated on a 0-3 scale and summed (range = 0-60). There are no subscales. Higher scores represent worse outcomes. The clinical cut-off is usually set at a score of 16; Beck Anxiety Inventory (BAI), a questionnaire measuring anxiety (Beck, Epstein, Brown, & Steer, 1988). 20 items are rated on a 0-3 scale and summed (range= 0-60). Higher scores indicate worse outcomes. There are no subscales. A score greater than 36 is considered to be clinically significant.; and Satisfaction with Life Scale, a questionnaire measuring overall life satisfaction and well-being (Diener, Emmons, Larsen, & Griffin, 1985). 5 items scored on a 1-7 scale and summed (Range = 5-35). Lower scores indicate worse outcomes. A score of 20 is considered neutral with higher scores considered increasingly more satisfied and lower scores considered increasingly more dissatisfied.

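### The SAP's plausibility caveat for an isolated significant result depends on an unstated expected direction, so a lone worsening on active is called implausible and a lone benefit of expected size is not

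*SAP*

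**What the plan says.** The SAP's Primary Outcomes section names four scales: "The four outcome measures include changes over the 6-month study period for the following scales". They cover burden, depression, anxiety and life satisfaction. The protocol's Outcome Measures section fixes which way is bad for each. For the Beck Anxiety Inventory, for example: "Higher scores indicate worse outcomes". Only on Satisfaction with Life is a lower score worse.

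The Analysis paragraph of the SAP's Statistical Methods treats two situations:

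- **Coherent results:** "we do not plan formal multiple comparison adjustments if the results fit a coherent pattern that is consistent with the context of similar studies".
- **Scattered results:** if just one scale, or very few, are significant and "their directions and/or magnitudes do not coherently fit with our a prior expectations, then we will note that the result(s" …) below 0.05 "lack plausibility and could be due to chance, despite meeting the conventional cutoff for statistical significance".

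The Design paragraph also says that "Bonferroni corrections will be used to control for Type I error resulting from multiple comparisons". That sentence follows one on breaking down significant effects, and how it relates to the four outcomes is not explained.

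No sentence states the expected direction. The nearest is the power statement, where the hypothesized Group tests "will have .80 power to detect a medium effect size (one-tailed, alpha = .05"). A one-tailed test of active against control implies an expected direction, and for a caregiver support system that direction can only reasonably be benefit.

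**The concern.** The trigger for the scattered-results caveat has two conditions joined by *and*: few scales are significant, and their direction or size does not match expectation. Suppose the active system raises caregiver anxiety and leaves the other three scales unchanged. One scale is significant in an unexpected direction, so both conditions hold and the report must call the result implausible. Now suppose anxiety improves by the same amount, with the same p-value, and that amount is in line with expectation. Only the first condition holds, so no caveat is required.

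How easily chance explains a lone p < 0.05 does not depend on its sign. Under the rule, though, the sign decides how the finding is described. The four scales are the only outcomes in the text available, and no adverse-event outcome is named there, so nothing else in that text would pick up a harm to the caregiver. Because the expectations are not recorded, they could also be supplied after the data are seen.

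**Working it through.** **Inputs.** 60 caregivers per arm (protocol, Randomization); alpha .05 and correlation .5 between visits (SAP, power statement); four outcomes (SAP, Primary Outcomes). Assumptions: medium means d = 0.5, or f = 0.25 for the interaction; complete data; correlation between outcomes from 0 to 0.7, since the documents give none.

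**1. The plan's own power figures.**

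- Group test: noncentrality = 0.5 × √(60/2) = 2.739.
- One-tailed .05, 118 df: critical t = 1.658, power 0.860 (normal approximation 0.863). The SAP says .80, so its figure is lower than its own inputs give.
- Two-sided .05: critical t = 1.980, power 0.775 (normal approximation 0.782), about 0.78.
- Interaction: noncentrality = 0.25² × 120 × 3 / (1 − 0.5) = 45 on 2 and 236 df, power above 0.999. This is consistent with the stated .99.

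These figures do not affect the labelling argument, but they are needed for the restated power.

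**2. Chance results by direction.** With four independent two-sided tests at .05 and no true effect:

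- P(at least one significant) = 1 − 0.95⁴ = 0.185.
- P(exactly one significant) = 4 × 0.05 × 0.95³ = 0.171.
- By symmetry, half are worsenings and half are benefits: 0.086 each.

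A simulation with 1,000,000 draws of four correlated z-statistics gives, for each direction:

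| Outcome correlation | Isolated worsening, null | Isolated benefit, null |
|---|---|---|
| 0 | 0.086 | 0.086 |
| 0.3 | 0.075 | 0.075 |
| 0.5 | 0.061 | 0.061 |
| 0.7 | 0.042 | 0.042 |

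**3. A true effect on one scale.** In the same simulation, with d = 0.5 worsening on one scale and none on the others, an isolated significant worsening appears with probability 0.69 to 0.72 over correlations 0 to 0.7. A true isolated benefit of the same size appears equally often. The direction condition labels all of the first and none of the second.

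**4. Would the planned test see the harm?** Take active-minus-control differences of 0, 0.5 and 0.5 SD at the three visits.

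- Mean difference = 1/3. Squared deviations: 1/9 + 1/36 + 1/36 = 1/6.
- Noncentrality = (60/2) × (1/6) / (1 − 0.5) = 10.
- F test on 2 and 236 df at .05: power 0.81.

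This is below the .99 in the SAP because the noncentrality is 10, not 45: the two calculations define the effect differently.

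**5. Evidence carried by a lone worsening.** The ratio of its probability under the harm to that under the null is 0.685/0.0855 = 8.0 at correlation 0 and 0.699/0.0607 = 11.5 at 0.5. At 0.7 it is 0.719/0.0422 = 17. An isolated worsening can be a chance result, but it is not implausible on these figures.

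**The case against.** The case against taking this far is substantial, and most of it stands as a limit on the point.

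- **The rule is only a caveat.** A reader might infer that a harm would be suppressed. The text does not say so: the result and its p-value are still reported, and descriptive summaries by group and time are planned.
- **A benefit can be labelled too.** The condition covers direction or size, so an isolated benefit of unexpected size is caught. The sentence is also set against a coherent pattern across outcomes, and one improved scale among three flat ones is not plainly such a pattern. But that case is then left without any label, whereas the lone worsening has one prescribed.
- **Only isolated results are affected.** If all four scales worsen by d = 0.5, three or four are significant with probability 0.75 to 0.79 (correlations 0.7 to 0), which is arguably outside the rule. The documents do not support saying that harm in general is discounted.
- **One-tailed does not mean blind to harm.** A reader might infer that the analysis cannot register a worsening. The word appears only in the power sentence; the stated treatment-effect analysis is the interaction F test, which has no direction.
- **The strength of evidence is easily overstated.** Dividing 0.81 by 0.05 gives about 16, but that compares one pre-named scale with its own error rate. The relevant event is an isolated worsening on any of four scales, for which the ratio is about 8 to 12 at correlations of 0 to 0.5.

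It can also be said that the root problem is the unsettled multiplicity rule. That rule does need settling, but settling it alone would not help: a worsening that survives adjustment could still be called implausible because of its direction.

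**Conclusion.** The point holds in a limited form. For results confined to one or very few scales, the SAP lets an unwritten expectation about direction decide whether a p < 0.05 finding is called implausible, although chance is equally likely in both directions (0.061 to 0.086 each at correlations of 0.5 to 0). A single-domain harm of 0.5 SD at both follow-ups would be detected with power of about 0.81 and then discounted in interpretation, though still reported.

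This rests on benefit being the expected direction, which is inferred, and on d = 0.5, complete data and three truly unaffected scales, which are assumed. That the four scales are the only place where harm could show is true of the text available; material ahead of the Statistical Analysis Plan heading was not part of it, so this cannot be fully confirmed. Neither document plans a formal safety conclusion, so a claim that such a conclusion is biased would go too far. What changes is how the report would interpret a worsening in one domain, and that is enough to justify correcting the wording.

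**What to change.** In the Analysis paragraph of the SAP's Statistical Methods:

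1. Remove direction from the trigger. Any isolated p < 0.05 result, benefit or worsening, gets the same statement that it could be due to chance, under the same multiplicity rule.
2. Report each such result with the active-minus-control difference and 95% CI at 3 and 6 months.
3. Describe an isolated worsening (higher Zarit, CES-D or BAI; lower Satisfaction with Life) as a possible harm, and do not call it implausible because of its direction.

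In the power statement, make the Group tests two-sided and give about 0.78 power for 60 per arm and d = 0.5, stating that this is what medium means.

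Barring the caveat for worsenings alone would not do: it would only reverse the asymmetry.

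**Cost.** SAP wording only, no new data. An isolated benefit will also carry the chance caveat. An occasional chance worsening will be reported as a possible harm: about 2.5% per scale, and up to 1 − 0.975⁴ = 9.6% for at least one of four if the scales are independent and unadjusted. The stated power falls slightly below .80; the real loss from a one-tailed to a two-sided test is from 0.86 to about 0.78.

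### The missing-data rule names no primary version, and one plausible reading of its group-mean filling would make the group-by-time test reject too often

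*SAP*

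**What the plan says.** The Missing Data paragraph (SAP, Statistical Methods) holds the only missing-data rule in the text available for review; one stretch of the SAP was not included. Its trigger is: "If subjects either cannot or refuse to complete surveys we will use a sensitivity analysis approach in dealing with these missing data". The two versions of the scores are: "with missing item interpolated using mean replacement by group, and 2) only using responses with 0% missing data". On disagreement: "If the results differ for the two approaches, then we will report on the differences". No version is given precedence.

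The Analysis paragraph sets the test that the rule feeds: "To evaluate the treatment effects, we will use repeated measures ANOVAs", and "an interaction term between treatment group and time will be included". On descriptive summaries it says: "These will be summarized overall, by treatment group, by assessment time, and by treatment group and time". The authors therefore distinguish an arm summary from an arm-by-visit summary, but the missing-data rule does not say which it means. The Design paragraph uses 'groups' for the two randomised conditions.

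**The concern.** Three things are left open.

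- **What is filled.** The trigger is a survey that is not completed; the remedy is for an item.
- **Which mean.** The arm is the natural meaning of 'group', but the mean could be taken at each visit or over all visits.
- **Which result decides.** Two p-values are produced per outcome, and nothing says which one supports the conclusion.

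The first two determine whether one of the planned analyses is valid. A missed survey filled with its arm's mean at that visit is counted as an observation but adds no information. The within-arm variance shrinks, the nominal sample size stays at 60 per arm, and the interaction test becomes anti-conservative. The third determines whether that result could carry the trial's conclusion.

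**Working it through.** **Inputs.** 60 caregivers per arm (Protocol, Randomization: "Sixty caregivers will be randomly assigned to the" active condition, the remaining 60 to control). Three visits, a 2 x 3 interaction test, r = .5 and alpha = .05 (SAP, Statistical Methods). The documents give no missing rate, so loss at months 3/6 is assumed at 5/10, 10/10, 10/20 and 20/30%.

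**The plan's own figure.** Taking a medium effect as f = 0.25, lambda = f² x N x m / (1 - r) = 0.0625 x 120 x 3 / 0.5 = 45. On 2 and 236 df, power is above .999, so the stated .99 is met. The set-up below uses the same test.

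**Why arm-by-visit filling inflates.** Take 20% loss at month 6: 48 of 60 are observed. Filled values have zero deviation, so the apparent variance is about 48/60 = 0.8 of the true one, and it is divided by 60 instead of 48. The apparent variance of that arm mean is therefore about 0.8 x 48/60 = 0.64 of its true value, and the standard error is 0.80 of what it should be. This shows the direction; simulation gives the size for the interaction test.

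**Type I error, whole surveys missed.** No treatment effect, compound symmetry, monotone loss completely at random, nominal 5%. There were 20,000 trials per scenario (simulation standard error √(.05 x .95/20,000) = 0.15 points), and 5,000 for the mixed model (random intercept, REML).

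| Loss at months 3/6 | Arm mean at that visit | Arm mean over all visits | Complete-case | Mixed model |
|---|---|---|---|---|
| 5/10% | 7.0% | 5.1% | 5.0% | 5.3% |
| 10/10% | 7.3% | 5.0% | 5.0% | 5.3% |
| 10/20% | 8.9% | 5.0% | 5.0% | 5.2% |
| 20/30% | 13.3% | 4.9% | 5.0% | 4.7% |

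Separately coded runs gave 7.1% at 5/10%, 9.1% at 10/20% and 12.3% at 15/30% for arm-by-visit filling. With r = .7 they changed by about half a point. With a common time trend of -0.3 SD by month 6, the pooled arm mean stayed at 4.7-5.5%.

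**The pooled mean under a real effect.** Suppose the arms differ by 0, 0.25 and 0.5 SD at the three visits, with 10/20% loss. The pooled difference is (1 x 0 + 0.9 x 0.25 + 0.8 x 0.5) / 2.7 = 0.23 SD. After filling, the month-6 difference is 0.8 x 0.5 + 0.2 x 0.23 = 0.45 SD, down from 0.50.

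**How often the two versions disagree (arm-by-visit filling).** With no effect, the filled version is significant and the 0%-missing version is not in 2.8, 2.9, 5.0 and 9.3% of trials per outcome; the reverse occurs in 0.6-1.1%. With the 0.25/0.5 SD effect the figures are 7, 8, 15 and 22%, against 2-3% in reverse.

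**Only items filled.** With arm-by-visit item means, an assumed inter-item correlation of 0.4, scales of 5, 12 and 20 items and 6,000 trials (standard error about 0.3 points), type I error is 5.4-5.7% at 1% of items missing, 5.3-5.6% at 2% and 6.6-7.0% at 5%. A separate 12-item run gave 6.0% at 2%.

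**Retention in the 0%-missing version.** If omissions are independent, the share kept is (1-p)^K per visit and (1-p)^(3K) across three visits, for K items. With 12 items at 2%: 0.98^12 = 78.5% and 0.98^36 = 48%. With 20 items at 2%: 67% and 30%. If one-fifth of caregivers make all the omissions, the three-visit share is 0.8 + 0.2 x (1-5p)^(3K), which is 80-89% over the scales and p = 1-5%.

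**Power for the 0.25/0.5 SD effect, mixed model against complete-case** (3,000 trials): 64.6 v 63.3, 63.5 v 62.4, 61.3 v 57.6 and 56.5 v 51.4%. The differences are 1.3, 1.1, 3.7 and 5.1 points; power with no loss is 67.7%.

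**The case against.** The inflation needs two readings that the SAP does not state: that whole surveys are filled, and that the mean is per visit. Taken literally, the remedy concerns an item, and at low item-missing rates the inflation is close to simulation noise. 'Group' is not really undefined either, since the Design paragraph ties it to the randomised arms. The rule is labelled a sensitivity analysis, both versions are run, and the 0%-missing version holds its level when data are missing completely at random, so a nominal-level result will be reported. Replacing the planned ANOVA by a mixed model also goes further than the defect requires.

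Much of this stands, and it rules out some stronger inferences. A reader might conclude that the SAP commits to an inflated test; the text permits that reading but does not force it. A reader might also take "Each significant interaction will be followed up with paired t-tests to examine treatment differences at each set of time points" to mean that every follow-up depends on the interaction. The Design paragraph also decomposes significant main effects, so the interaction is not the only gate. Nor can heavy loss in the 0%-missing version be assumed: it depends on whether the criterion applies per visit or across visits, and on how omissions cluster.

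What the objection does not remove is the lack of precedence. The trigger is an uncompleted survey, and no other available rule covers one. Reporting both results discloses a disagreement without saying which result decides.

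**Conclusion.** The concern holds as an ambiguity with a conditional consequence. Two score versions are planned, neither is primary, and the level of filling and the visit dimension of the mean are not stated. If, and only if, whole missed surveys are filled with the arm mean at that visit, the 5% group-by-time test runs at about 7, 9 and 13% at assumed losses of 5/10, 10/20 and 20/30%. Pooling over visits protects the level but dilutes a real month-6 difference. Item-only filling costs about a point or less at 1-2% of items missing.

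These figures assume 60 per arm, r = .5 and missingness completely at random. Bias from outcome-related loss was not quantified for any version. The point should be fixed because the remedy is cheap; confidence is medium because the inflation depends on the reading.

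**What to change.** Drop arm-mean replacement and replace the rule with wording such as:

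> The primary analysis of each outcome is a linear mixed model with condition, time and condition x time, fitted by likelihood to every observed visit of all randomised caregivers. Missed surveys are not filled. An isolated missing item is prorated from the respondent's own answered items on that scale, subject to a pre-stated minimum number answered; otherwise the scale is missing at that visit. Complete-case analysis is a sensitivity analysis. Conclusions rest on the primary analysis.

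The sponsor should set the item minimum and the covariance structure in advance.

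If the classical ANOVA is kept, the minimum change is to leave missed surveys unfilled, define the item rule, and name the complete-case version as primary. That version needs a stronger missingness assumption than the mixed model and, in the scenarios above, loses about 1 to 5 points of power relative to it.

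The cost is SAP wording and standard software, with no extra data or visits. Standard errors will be slightly wider than arm-by-visit filling would show, and the mixed model still assumes that missingness depends only on observed data.
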